## 5. AMENDMENTS AND UPDATES

NONE

## 6. MILESTONES

Milestone	Planned date
Start of data collection	November 2020
End of data collection	January 2021
Study Report	February 2021
Manuscript/Conference abstract	April 2021

## 7. RATIONALE AND BACKGROUND

Breast cancer is the leading cause of cancer-related death in females worldwide. An approximately 1.7 million new cases of breast cancer were diagnosed in 2012, contributing to 12% of all newly diagnosed cancers worldwide. According to estimates of Globocan 2012, India, United States and China collectively accounts for almost one third of the global breast cancer burden. The reported increase in the rate of incidence and mortality due to breast cancer in India was 11.54% and 13.82%, respectively during 2008-2012. Among Indian females also breast cancer has been ranked the number 1 cancer with age adjusted rate as high as 25.8 per 100,000 women and mortality rate of 12.7 per 100,000 women. The age adjusted incidence rate of carcinoma of the breast was found as high as 41 per 100,000 women for Delhi, followed by Chennai (37.9), Bangalore (34.4) and Thiruvananthapuram (33.7) district. Breast cancer survival rates have increased over the last 50 years, as relative survival increased from 75.2% in 1975 to 90.6% in 2008. The 5-year survival rate for women with stage 0/I breast cancer is near to 100%, compared to that of stage II and III, which are 93% and 72% respectively. Women who are diagnosed with metastatic or stage IV breast cancer have a much lower 5-year survival rate of 22%.

An increased understanding of breast cancer has enabled enhanced profiling of different disease subtypes. Subtype classification is essential to decide on the appropriate treatment regime. Breast tumors are grouped according to the expression of hormone receptors (HR) and human epidermal growth factor receptor 2 (HER2). An approximately 75% of all breast cancer tumors are diagnosed to be HR positive (HR+) which grow in response to increased levels of the hormones estrogen and progesterone. HER2 positive (HER2+) breast tumors grows more aggressively than HER2 negative (HER2-) tumors and represent around 15% of all breast tumors. The standardized incidence rates of HR+/HER2- breast cancer was 75.21 per 100,000 women in 2012 across the world which accounted for 67.3% of all subtypes.

Over the past few decades, hormonal therapies such as letrozole and fulvestrant have emerged as the preferred treatment for HR+ breast cancers. Following the success of the phase II PALOMA (Palbociclib: Ongoing Trials in the Management of Breast Cancer)-1 trial, the United States Food and Drug Administration (USFDA) granted accelerated approval of the CDK4/CDK6 inhibitor palbociclib that causes cell cycle arrest to be used in combination with letrozole to treat advanced/metastatic HR+/HER2- post-menopausal breast cancer, making it the first CDK 4/6 inhibitor approved in breast cancer. The PALOMA-1 trial demonstrated median progression-free survival of 20.2 months for post-menopausal patients with advanced/metastatic HR+/HER- breast cancer receiving letrozole in combination with palbociclib vs. 10.2 months in patients receiving letrozole and placebo. The follow up phase III PALOMA-2 trial demonstrated median progression free survival of 24.8 months for post-menopausal patients with advanced/metastatic HR+/HER- breast cancer receiving letrozole in combination with palbociclib vs. 14.5 months in patients receiving letrozole and placebo.

In October 2016, palbociclib was granted approval to be used in combination with fulvestrant by the USFDA. This was following the success of the Phase III PALOMA-3 trial, conducted in patients with advanced/metastatic HR+/HER- breast cancer that had relapsed or progressed during endocrine therapy. The PALOMA-3 trial demonstrated a median progression-free survival of 9.5 months in those receiving fulvestrant in combination with palbociclib vs. 5.6 months in patients receiving fulvestrant with placebo.

Palbociclib in combination with letrozole was approved in August 2016 by the Central Drugs Standard Control Organization (CDSCO) for the treatment of postmenopausal women with estrogen receptor (ER) positive, human epidermal growth factor receptor 2 (HER2) negative advanced breast cancer as initial endocrine- based therapy for their metastatic disease. Palbociclib was also granted approval to be used in combination with fulvestrant in December 2017 by the CDSCO for the treatment of HR+/HER2- advanced or metastatic breast cancer in women with disease progression following endocrine therapy.

Palbociclib has been approved in India for over 3 years, based on the results of 3 multinational PALOMA trials, but significant data on the clinical utility of palbociclib combination in routine clinical practice and outcomes associated with palbociclib use are not available. Therefore, real world data on the characteristics, treatment patterns and clinical outcomes among patients receiving palbociclib combinations to treat HR+/HER- ABC/MBC will provide valuable insight to help inform treatment decisions.

PFIZER CONFIDENTIAL

## 8. RESEARCH QUESTION AND OBJECTIVES

The primary objective of this real-world study is to describe patient demographics, clinical characteristics, treatment patterns and clinical outcomes of adult female patients who have received palbociclib combination treatments for HR+/HER2- ABC/MBC in real world settings in India:

- Palbociclib in combination with aromatase inhibitor (as prescribed by the Physician) for the treatment of postmenopausal women with HR+/HER2- advanced breast cancer as initial endocrine-based therapy for their metastatic disease.
- Palbociclib for the treatment of hormone receptor HR+/HER2- advanced or metastatic breast cancer in combination with fulvestrant in women with disease progression following endocrine therapy.

### Primary objectives

- To describe the demographics and clinical characteristics of patients who have received palbociclib combination with aromatase inhibitor (as prescribed by the Physician) in menopausal state as initial endocrine therapy in MBC or with fulvestrant after progression on prior endocrine therapy.
- To summarize adjuvant therapies received for the treatment of early or locally advanced breast cancer (Stages 0-IIIa).
- To describe treatments received in the advanced/metastatic setting, before and after palbociclib combination use.
- To describe dosing and dose changes, interruptions, delays, and discontinuations associated with palbociclib use in clinical practice.
- To describe supportive therapies received by patients while receiving palbociclib combination treatments.
- To determine in overall population and defined subgroups, clinical outcomes including (but not limited to):
  - Proportion of patients who are progression free at specific intervals (eg, 6, 12, 18 months).
  - Objective response rate (ORR) - depending on availability of follow-up data.
  - Proportion of alive patients 1 and 2 years post palbociclib combination initiation - depending on availability of follow-up data (sample size permitting).

## 9. RESEARCH METHODS

### 9.1 Study Design

This is a post marketing, retrospective, non-interventional study (NIS). The study will be conducted as a retrospective medical record review of patients who have received palbociclib combination with aromatase inhibitor (as prescribed by the Physician) in menopausal state as initial endocrine therapy in MBC or with fulvestrant after progression on prior endocrine therapy. It will comprise of an initial screening and eligibility assessment of patients followed by data collection from eligible patient records.

Data collection will be conducted using a predesigned electronic case report form (eCRF). Eligible physicians will be invited to complete the eCRF of patients that meet the study criteria. Each eCRF will take around 25 minutes to complete. Patient eligibility will be confirmed by treating physicians. In order to allow for a sufficiently long observational window, treating physicians will be asked to go back to a specific point in time, the index date, and sequentially select the medical records of the next 'n' patients who meet the inclusion criteria. The 'index date' will be defined as 60 days after the physician first prescribed palbociclib + partner therapy following the availability of specific indication in the market (eg, if palbociclib + aromatase inhibitor was available on 25 October 2016 in India and the physician initiated a patient on palbociclib with aromatase inhibitor the next day, the index date will be 26 December 2016). The index date will differ for the specific indications/combination partners if approved on different dates.

The proportion of patients treated in accordance with the first line versus second or later line setting for metastatic disease will be approximately 7:3, as has been observed in the real world practice.

The advantage to a retrospective medical record review approach over a database analysis is that of being designed specifically to collect data that fulfils the study objectives. Thus, it readily collects and informs on all key drug related clinical outcome measures of critical importance to this study, in a consistent manner, across countries. The resulting data set enables direct comparisons across markets, delivering in turn greater confidence in the reliability of conclusions drawn from the research. An additional advantage of this approach lies in the ability to obtain information that only the treating physician may be aware of, such as the reasons for treatment switches or discontinuations or more perceptive questions that rely on the physicians' professional opinion.

## 9.2 Setting

Data will be collected from approximately 10 physicians recruited across India. Each physician will complete at least 10-15 eCRFs. Data will be collected retrospectively at a single point in time from patient medical records.

Initial screening questions/recruitment criteria will ensure the relevant physicians are selected and all other non-qualifying physicians will be excluded. In addition, during physician recruitment a representative geographical split and private/public practice split will be sought where possible to ensure a representative sample.

To be eligible, physicians must have treated or be treating 10 or more HR+/HER2- ABC/MBC patients who meet the eligibility criteria for the study. This will ensure that recruited physicians will be able to complete the minimum number of eCRFs required to participate in the study. Once physicians have been recruited, they must go back to a specific index date, defined in [Section 9.1](#) and select the next number of eligible patient records from patients who have been treated with a palbociclib combination. The consecutive approach to recruitment will be stressed to each participating physician to limit selection bias.

Each participating physician and patient must meet the following criteria to be eligible for the medical record reviews.

### 9.2.1 Inclusion Criteria

#### Physician inclusion criteria

- Oncologist.
- Responsible for treating  $\geq 10$ ABC/MBC patients who meet the eligibility criteria.
- Agrees to participate in the study and complete the eCRFs within the data collection period.

#### Patient inclusion criteria

Patients must meet all of the following inclusion criteria to be eligible for inclusion in the study:

- $\geq 18$  years old females.
- HR+/HER2- breast cancer diagnosis with confirmed metastatic or advanced disease.
- Received palbociclib with aromatase inhibitor (as prescribed by the Physician) as initial endocrine therapy in postmenopausal MBC patients or with fulvestrant in patients who have progressed on prior endocrine therapy

- Patients on LHRH agonists for ovarian function suppression in pre- or perimenopausal stage only if prescribed palbociclib with fulvestrant.
- No prior or current enrolment in an interventional clinical trial for ABC/MBC.
- Minimum of 3 months of follow up data since palbociclib with fulvestrant initiation, or minimum of 6 months of follow up data since palbociclib with aromatase inhibitor initiation.

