**Population:** Data will be collected from the Indian routine clinical practice settings. Approximately 10 oncologists will be included. To be eligible to participate, physicians must have treated, or be treating 10 or more HR+/HER2- ABC/MBC patients with palbociclib combination with aromatase inhibitor (as prescribed by the Physician) in menopausal state as initial endocrine therapy in MBC or with fulvestrant after progression on prior endocrine therapy. Each physician will complete at least 10-15 electronic case report forms (eCRFs). Included physicians must go back in their records to the specific index date and select the next number of eligible patients for which they will complete eCRFs. The 'index date' will be defined as 60 days after the physician first prescribed palbociclib + partner therapy following the availability of specific indication in the market. To be eligible, patients must be females, aged 18 or over, have been diagnosed with HR+/HER2- ABC/MBC and must have received palbociclib combination with aromatase inhibitor (as prescribed by the Physician) as initial endocrine therapy in postmenopausal MBC patients or with fulvestrant in patients who have progressed on prior endocrine therapy. For the study, patients must have initiated palbociclib with fulvestrant a minimum of 3 months, or palbociclib with aromatase inhibitor a minimum of 6 months prior to data collection.

**Variables:** The variables assessed in this study will be patient demographics at the time of data collection, clinical characteristics, comorbid conditions, early and advanced breast cancer treatment history, palbociclib treatment patterns including dose changes, clinical outcomes and date of death if applicable.

**Data sources:** Patient medical records will be used as the data source for the study.

**Study size:** Approximately 10 physicians will be recruited across the India; this will enable data to be collected for approximately 150 patients.

**Data analysis:** All analyses will be descriptive in nature. Categorical variables will be described using the number of observations and number and percent (%) in each category.

Numeric variables will be described using the number of observations, mean and standard deviation, and minimum, maximum, median and interquartile range. Time to event will be described using a Kaplan-Meier chart for the median.

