### 9.3 Variables

**Table 1. List of Study Variables**

Variable	Role	Data Source(s)	Operational Definition
Patient demographics	Baseline Sub-group identifier	Patient records	Age, ethnicity, weight, height, biomarker status, family history of breast cancer.
Clinical characteristics	Baseline Sub-group identifier	Patient records	Time since diagnosis, staging, node status, menopause status. ECOG/Karnofsky functional status, diagnosis for which palbociclib combination was prescribed, sites of metastases, de novo vs. recurrent disease.
Comorbid conditions	Baseline Sub-group identifier	Patient records	Comorbid conditions.
Early treatment history	Baseline Sub-group identifier	Patient records	Adjuvant treatments received since breast cancer diagnosis, time since end of adjuvant treatment, surgery/radiotherapy received.
Advanced treatment history	Baseline Sub-group identifier	Patient records	Treatments and supportive therapies received since metastatic/advanced HR+/HER2- diagnosis, duration of treatments, reasons for regimen changes.
Palbociclib combination treatment	Exposure Sub-group identifier	Patient records	Starting dose, duration of treatment, line of treatment, changes in dose, interruptions, cycle delays and discontinuations; where possible reasons for change in treatment.
Clinical outcomes	Outcomes	Patient records	Proportion progression free, ORR, TTP, PFS, patient death, 1-year and 2-year survival in all patients and within specific subgroups.

PFIZER CONFIDENTIAL

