## **9.7 Data Analysis**

Detailed methodology for summary and statistical analyses of data collected in this study will be documented in a statistical analysis plan (SAP), which will be dated, filed and maintained by the sponsor. The SAP may modify the plans outlined in the protocol; any major modifications of primary endpoint definitions or their analyses would be reflected in a protocol amendment.

All analyses are to be descriptive and so all methods to be used will reflect this descriptive nature. The specific method that will be used depends on type of variable being analyzed and those methods are:

- Categorical variables – will be described using:
  - Number of observations (n);
  - Number and percent (%) within each category;
  - Number of missing observations.
- Numeric variables – will be described using:
  - Number of observations (n);
  - Mean & Standard deviation;
  - Minimum, Maximum, Median and 1st & 3rd Quartiles;
  - Number of missing observations.

PFIZER CONFIDENTIAL

- Time to event – will be described using:
  - A Kaplan-Meier chart that will visually estimate the distribution of times to some events, eg, progression, and will consider those patients for which the event has not yet occurred;
  - 1-year and 2-year rates, median or some more appropriate percentiles if the median time is not reached in the sample.

Missing data will be excluded on a case by case basis and will not be imputed. This will mean that each table will not necessarily be based on the same number of patients.

All statistical analyses will be conducted with general purpose statistical software (SAS) version 9.0 or higher

PFIZER CONFIDENTIAL

Palbociclib

A5481145, PD-0332991 NON-INTERVENTIONAL STUDY PROTOCOL

Final Protocol version 1.0, 19-Oct-2020

CCI

PFIZER CONFIDENTIAL

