- Received palbociclib with aromatase inhibitor (as prescribed by the Physician) as initial endocrine therapy in postmenopausal MBC patients or with fulvestrant in patients who have progressed on prior endocrine therapy.
- Patients on LHRH agonists for ovarian function suppression in pre- or perimenopausal stage only if prescribed palbociclib with fulvestrant.
- No prior or current enrolment in an interventional clinical trial for ABC/MBC.
- Minimum of 3 months of follow up data since palbociclib with fulvestrant initiation, or minimum of 6 months of follow up data since palbociclib with aromatase inhibitor initiation

Exclusion criteria

[figure not shown]
[figure not shown]
Patients meeting any of the following criteria will not be included in the study:

- Cancers other than breast cancer
- Male breast cancer
- Indications other than mentioned in the protocol
- Visceral crisis

Treatment/cohort labels

Palbociclib

PFIZER CONFIDENTIAL

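### The abstract asks for time elapsed since starting palbociclib, whereas section 9.2.1 and the SAP ask for observed follow-up; read literally, the second rule drops early deaths and inflates survival counted from initiation.

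*Protocol*

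**What the plan says.** Two time rules appear, with the same thresholds.

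- **Elapsed time.** Protocol section 4 (Abstract, Population) says of those to be included that they "must have initiated palbociclib with fulvestrant a minimum of 3 months, or palbociclib with aromatase inhibitor a minimum of 6 months prior to data collection". Neither vital status nor length of observation enters.
- **Observed follow-up.** Protocol 9.2.1 (Patient inclusion criteria) says "Minimum of 3 months of follow up data since palbociclib with fulvestrant initiation, or minimum of 6 months of follow up data" with an aromatase inhibitor (AI). SAP 2.1 repeats this for AI as "minimum of 6 months of follow up data since palbociclib with aromatase inhibitor initiation", and likewise for fulvestrant.

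The second rule is the operative one. Protocol 9.2 introduces the list with "Each participating physician and patient must meet the following criteria to be eligible for the medical record reviews", and every criterion on it is mandatory. Neither document says that a patient who died inside the window counts as having enough follow-up.

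The outcomes run from the start of treatment. The objectives include "Proportion of alive patients 1 and 2 years post palbociclib combination initiation", together with progression-free proportions at, for example, 6, 12 and 18 months. Protocol Table 1 lists "1-year and 2-year survival in all patients and within specific subgroups". Protocol 9.7 plans Kaplan-Meier curves with "1-year and 2-year rates, median or some more appropriate percentiles if the median time is not reached in the sample". The readable text describes no landmark or delayed-entry analysis; parts of protocol 9.7 and of the SAP's outcome section and shells are redacted.

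**The concern.** A criterion that needs 3 or 6 months of observed data conditions entry on surviving that long, while the clock for survival starts at month 0. The deaths that would pull the curve down first are never entered.

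The loss would be hard to see. Under protocol 9.1 each physician takes records in sequence until the required number of eligible patients is reached, so a skipped early death is replaced by the next eligible record and the total stays near 150. The readable SAP table list has no screening or disposition table. Protocol 9.9 names groups that will not be represented, but not this one.

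The windows also differ by partner drug. The SAP tabulates results by first versus later line; to the extent that regimen follows line, the distortion would be unequal between the columns.

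At stake are the survival and progression-free parts of the sixth primary objective. The other objectives do not estimate survival.

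**Working it through.** **The plan's own figure.** The documents state no expected survival, power or precision, so only Table 2 can be reproduced: 20+10+40+20+10+10+20+20 = 150 records and 1+1+2+2+1+1+1+1 = 10 physicians. Both totals agree.

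**One patient under both rules.** She starts palbociclib with an AI a year before data collection and dies in month 2. Under the abstract she is eligible, because 12 months have elapsed and 12 ≥ 6. Under 9.2.1 and SAP 2.1 read literally she is not, because she has 2 months of data and 2 < 6. The rules are therefore not equivalent.

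**Direction.** Let S(t) be survival from initiation and L the threshold (6 months AI, 3 months fulvestrant). With early deaths excluded and no losses, the study estimates S(t)/S(L) for t ≥ L. This exceeds S(t) whenever anyone dies before L.

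**Share of early hazard removed.** With cumulative hazard proportional to t^k, the share of the first year's cumulative death hazard removed is (L/12)^k. No death rate is needed.

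| k | AI, L = 6 | Fulvestrant, L = 3 |
|---|---|---|
| 0.8 | 57% | 33% |
| 1 (constant hazard) | 50% | 25% |
| 1.5 | 35% | 12.5% |

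**Size, for illustration only.** The assumptions, none from the documents, are a constant hazard within regimen, no losses, and early deaths of 2% to 10% (AI, by month 6) and 1% to 5% (fulvestrant, by month 3). The regimens are pooled 7:3; protocol 9.1 gives that ratio for line of treatment, so it is only a proxy for regimen.

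- Low case, 1 year, all starters: AI 0.98² = 0.9604; fulvestrant 0.99⁴ = 0.9606; pooled 0.9605. Literal rule: 0.98 and 0.99³ = 0.9703; pooled 0.9771. Difference +1.7 points.
- High case, 1 year, all starters: AI 0.90² = 0.8100; fulvestrant 0.95⁴ = 0.8145; pooled 0.8114. Literal rule: 0.90 and 0.95³ = 0.8574; pooled 0.8872. Difference +7.6 points.
- At 2 years: low 0.9225 to 0.9385 (+1.6); high 0.6583 to 0.7198 (about +6.2).

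**Progression-free proportions.** Early progression alone excludes nobody, so the divisor is again overall survival S(L), now acting on a smaller proportion. With the trial medians in protocol section 7 (24.8 and 9.5 months) and a constant hazard, 12-month values are 2^(−12/24.8) = 0.715 and 2^(−12/9.5) = 0.417, pooled 0.626. Dividing by S(L) gives 0.637 (low, +1.1) and 0.688 (high, +6.2).

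**Is the high case plausible?** With a 24.8-month median, 1 − 2^(−6/24.8) = 15.4% of AI patients have progressed or died by month 6. Ten percent dead by then equals 10/15.4 = 65% of that total, which looks too large, all the more since visceral crisis is an exclusion (9.2.2).

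**The case against.** The strongest reply is that potential follow-up was meant. The abstract uses the same two thresholds as time before data collection. Protocol 9.1 explains the look-back to an index date as a way to secure a long enough observation window. Death is collected as an outcome, and a patient who died in month 2 has a fully known outcome. Protocol 9.9 leaves further definition of patient selection to the eCRF, which is not available here. This reading is plausible, and under it there is no bias. It does not make the wordings equivalent: treating physicians confirm eligibility themselves, no routine source data verification is planned (9.8), and a reader of the report could not tell which rule was used.

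A second reply is that the reach is uncertain. The readable SAP shows response categories, response and clinical benefit rates and a count of deceased patients, but no Kaplan-Meier or 1- and 2-year survival analysis, and redactions prevent a check. The protocol also makes the survival proportions contingent on available follow-up and numbers. This stands as a limit. It does not settle how early deaths are handled, and the protocol still lists survival among its outcomes.

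A third point concerns losses. The literal rule also removes patients lost early. If their loss is informative, leaving them out may push survival or progression-free estimates either way.

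A reader might also infer a shift of about ten points from section 7: "Women who are diagnosed with metastatic or stage IV breast cancer have a much lower 5-year survival rate of 22" percent. The documents do not support that use. The figure is general stage IV background counted from diagnosis. With a constant hazard it implies 1 − 0.22^(6/60) = 14.1% of AI patients dead by month 6, nearly all of the 15.4% progressed or dead implied by the 24.8-month median. With a Weibull shape of 0.8 it implies 21.3%, more than that total. The trial medians may be optimistic for routine practice, but the two sources cannot be combined as if they described the same patients.

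**Conclusion.** The concern holds in conditional form. The abstract and the operative criteria state non-equivalent rules, and the documents do not say which governs early deaths. If 9.2.1 and SAP 2.1 are applied literally, excluding early deaths biases 1- and 2-year survival upward by the factor 1/S(L), with the longer window for AI. Progression-free proportions move by fewer points, through early deaths and any informative early losses. The upward direction is certain for deaths only.

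The size cannot be derived from the documents. The illustrative range at 1 year is about 1.7 to 7.6 points, resting on assumed early deaths, a constant hazard, no losses and a 7:3 mix borrowed from line of treatment; its upper end is probably too high.

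It would go too far to conclude that the study did exclude early deaths. The text permits that reading but does not establish it.

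**What to change.** Use one rule in the protocol abstract, protocol 9.2.1 and SAP 2.1, taking the abstract's form: palbociclib with fulvestrant started at least 3 months, or with an AI at least 6 months, before the data-collection date, regardless of vital status or length of observed follow-up. State that early deaths count as events and that losses are censored at last contact. Date of death is already a study variable, so no new data item is needed.

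Selection may already be complete: collection was due to end in January 2021, and the SAP rests on a CRF dated 20 May 2021. If records were selected under the follow-up-data rule, report the number excluded for short follow-up by reason (death, loss, other) where sites recorded it. Label survival and progression-free results as conditional on 3 or 6 months of follow-up, and add this selection to section 9.9. No re-screening of charts is needed.

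The cost is a wording amendment with ethics approval under section 10.3, or, for the fallback, some text and a table row. Under the single rule some patients will contribute little dosing and treatment-pattern data, and outcome figures will look slightly less favourable.
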